**SC WEEK #13 CLINIC VISIT & PK ASSESSMENT FOR SC DOSING**

The following procedures and tests will be completed at the SC Week #13 visit:

- Abbreviated physical exam with inspection of SC injection sites and Specific Signs/Symptoms Check.
- If the following Specific signs/symptoms are present perform Wells Score and blood draw for D-dimer testing ([Appendix 4](#); see also [Section 3.6.3.3](#)):
- a. Clinical suspicion of possible DVT with unilateral symptomatic leg swelling, accompanied by any of the following pain, warmth, and/or redness
  - b. Medical suspicion of possible PE in a subject presenting with new or worsening dyspnea, tachypnea, chest pain, syncope, and cough in the appropriate clinical setting (cough should not be due to infection, lung disease [eg, asthma, emphysema], or angiotensin-converting enzyme inhibitors)
  - c. Any single alarm symptom such as hemoptysis or cyanosis ([36,37,38](#))
- Vital signs (pre-infusion: SBP, DBP, HR, T, RR)

- Predose blood draw for trough total IgG
- Body weight
- Observe patient/caregiver self-administration of SC infusion of IGSC 20% in the clinic and initiate serial PK sampling as detailed below
- Concomitant medications
- Adverse events including SBIs  
Note: Record any SBIs (defined in [Appendix 2](#)), hospitalizations due to infections, and non-serious infections (by category) as detailed in [Section 3.6.3.1](#).
- Record days lost from work/school/daily activities due to infections and treatment
- Review SC infusion diary and infusion details with subjects/caregivers.

PK samples associated with the SC administration of IGSC 20% will commence at the SC Week #13 visit for all enrolled subjects including those  $\leq 5$  years of age. Subjects between the ages of 2 to 5 years of age will undergo an abbreviated schedule for serial PK sampling.

Blood draws for PK assessment **for subjects >5 years of age** will be taken at the following times:

- Prior to the 13th SC infusion (within 0.5 h of the start of infusion and this is the same sample for predose trough total IgG level)
- 1 day  $\pm$  4 h post-infusion
- 3 days  $\pm$  4 h post-infusion
- 4 days  $\pm$  4 h post-infusion
- 5 days  $\pm$  4 h post-infusion
- 7 days  $\pm$  1 day post-infusion (within 0.5 hour prior to the 14th SC dose) for IgG trough level

Blood draws for PK assessment **for subjects  $\leq 5$  years of age** will be taken at the following times:

- Prior to the 13th SC infusion (within 0.5 h of the start of infusion and this is the same sample for predose trough total IgG level)
- 3 days  $\pm$  4 h post-infusion
- 7 days  $\pm$  1 day post-infusion (within 0.5 hour prior to the 14th SC dose) for IgG trough level

The actual date/clock time of the start and end of the SC infusion, volume/amount of dose infused, rate of infusion, and location and number of infusion sites will be recorded. The actual date/clock time for each blood sample for either PK or trough level assessment will be collected and recorded. The interim PK samples may be obtained at an alternate location. If an outside agency is utilized for sample collection, the sample will be drawn and processed per protocol and laboratory manual instructions.

**SC WEEK #14 CLINIC VISIT**

The following procedures and tests will be completed at the SC Week #14 visit:

- Abbreviated physical exam with inspection of SC injection sites and Specific Signs/Symptoms Check.  
If the following Specific signs/symptoms are present perform Wells Score and blood draw for D-dimer testing ([Appendix 4](#); see also [Section 3.6.3.3](#)):
  - a. clinical suspicion of possible DVT with unilateral symptomatic leg swelling, accompanied by any of the following pain, warmth, and/or redness
  - b. medical suspicion of possible PE in a subject presenting with new or worsening dyspnea, tachypnea, chest pain, syncope, and cough in the appropriate clinical setting (cough should not be due to infection, lung disease [eg, asthma, emphysema], or angiotensin-converting enzyme inhibitors)
  - c. Any single alarm symptom such as hemoptysis or cyanosis ([36,37,38](#))
- Vital signs (pre-infusion: SBP, DBP, HR, T, RR)
- Predose blood draw for trough total IgG prior to SC infusion (within 0.5 hour prior to the start of infusion). Note: This trough IgG sample is the same one that is used for PK blood draw at 7 days post-infusion timepoint (SC Week#13).
- Observe subject/caregiver self-administration of SC infusion of IGSC 20% in the clinic
- Concomitant medications
- Adverse events including SBIs  
Note: Record any SBIs (defined in [Appendix 2](#)), hospitalizations due to infections, and non-serious infections (by category) and antibiotic treatment as detailed in [Section 3.6.3.1](#).
- Record days lost from work/school/daily activities due to infections and treatment
- Review SC Infusion Diary and infusion details with subjects/caregivers

**3.6.2.5 Monthly Extension Visits**

The monthly extension visits will occur only for subjects enrolled early in the trial who may complete their regularly scheduled 24 weeks of SC therapy on the initial IGSC 20% dose before a decision from the interim PK analysis is available. In this event, these subjects will continue to receive weekly SC infusions of IGSC 20% until the interim PK analysis deems whether or not a new dose adjustment factor would be required. Subjects will return to the study center every 4 weeks for evaluation and have the same study procedures performed as those at SC Week#21. At every 8 weeks, safety laboratory assessments, IgG subclass levels, and specific antibody titers for *S. pneumoniae*, *H. influenzae*, and *C. tetani* (tetanus) will be performed. This will continue until the interim PK analysis is completed (See [Section 3.1.5](#)).

The following procedures and tests will be completed at the Monthly Extension Visit:

- Abbreviated physical exam with inspection of SC injection sites and Specific Signs/Symptoms Check.

If the following Specific signs/symptoms are present perform Wells Score and blood draw for D-dimer testing ([Appendix 4](#); see also [Section 3.6.3.3](#)):

- a. Clinical suspicion of possible DVT with unilateral symptomatic leg swelling, accompanied by any of the following pain, warmth, and/or redness
  - b. Medical suspicion of possible PE in a subject presenting with new or worsening dyspnea, tachypnea, chest pain, syncope, and cough in the appropriate clinical setting (cough should not be due to infection, lung disease [eg, asthma, emphysema], or angiotensin-converting enzyme inhibitors)
  - c. Any single alarm symptom such as hemoptysis or cyanosis ([36,37,38](#))
- Vital signs (pre-infusion: SBP, DBP, HR, T, RR)
  - Body weight (will be used for SC dose calculation) and height
  - **Every 8 week intervals only:** Predose laboratory assessments drawn prior to SC infusion (as outlined in screening visit [[Section 3.6.2.1](#)] including hematology, clinical chemistry, special tests, and urinalysis) **and** IgG subclass, and antibody titers for *S. pneumoniae*, *H. influenzae*, and *C. tetani* (tetanus) prior to SC infusion (within 0.5 hour prior to the start of infusion)
  - Predose blood draw for trough total IgG
  - Observe subject/caregiver self-administration of SC infusion of IGSC 20% in the clinic
  - Concomitant medications
  - Adverse events including SBIs
- Note: Record any SBIs (defined in [Appendix 2](#)), hospitalizations due to infections, and non-serious infections (by category) as detailed in [Section 3.6.3.1](#).
- Record days lost from work/school/daily activities due to infections and treatment
  - Review SC infusion diary and infusion details with subjects/caregivers

If the results of the interim PK analysis do not indicate a need for a dose adjustment factor change, subjects will be brought into the clinic (within one week following the confirmation of the initial dose adjustment factor) and end of study procedures will be performed.

#### 3.6.2.6 Final Visit (Week #25)/Early Termination Clinic Visit

The Final Visit (Week #25) visit will be scheduled one week after the final SC infusion. If a subject discontinues at any point during the study after the first Run-In visit or IV#1 for those who enter the IV Phase directly, the subject will be requested to return to the Investigator's study site for an Early Termination Visit. The assessments at this visit will be the same as the Final Visit in the case a subject who prematurely discontinues the study.

The following procedures and tests will be completed (note that no study-related infusion will be scheduled):

- Full physical exam (excludes breast and genitourinary exam)
- Vital signs (SBP, DBP, HR, T, RR)

- Laboratory assessments (as outlined in Screening Visit [[Section 3.6.2.1](#)] including hematology, clinical chemistry, special tests, and urinalysis)
  - Blood draw for trough total IgG, IgG subclass, and antibody titers for *S. pneumoniae*, *H. influenzae*, and *C. tetani* (tetanus)
  - Serum pregnancy test (for females of childbearing potential)
  - Measles antibody titer
  - Concomitant medications
  - Adverse events including SBIs
- Note: Record any SBIs (defined in [Appendix 2](#)), hospitalizations due to infections, and non-serious infections (by category) as detailed in [Section 3.6.3.1](#).
- Record days lost from work/school/daily activities due to infections and treatment
  - Review SC infusion diary and infusion details with subjects/caregivers

### 3.6.3 Description of Laboratory Tests and Procedures

Detailed descriptions of laboratory test procedures are located in the study Laboratory Manual. [Table 3-2](#) provides a summary of the laboratory tests conducted for this study.

**Table 3-2 Name, Description, and Location of Laboratory Tests and Procedures**

Test Panel	Description	Location
Hematology a	Hemoglobin, hematocrit, platelets, red blood cell count including red blood cell morphology, white blood cell count with differential; ARC	Central
Additional special tests a	DAT, serum free hemoglobin, haptoglobin	Central
D-dimer	D-dimer	Central
Chemistry a	Sodium, potassium, creatinine, chloride, calcium, BUN, bicarbonate, albumin, LDH, AST, ALT, ALP, glucose, total bilirubin, indirect bilirubin	Central
IgG levels a	Total IgG levels will consist of trough (pre-dose) measurements in all subjects, and for PK profiling of IGIV-C 10% (IV Phase) and IGSC 20% (SC Phase)	Central
IgG subclass levels and antibody titers a	Measurement of IgG subclasses (IgG1, IgG2, IgG3, IgG4). Measurement of levels of selected specific antibodies against H. influenzae , anti-pneumococcal polysaccharide ( S. pneumoniae ), and C. tetani (tetanus)	Specialty
Trough measles antibody titers (functional assay) a	Trough samples for measles antibody titer will be collected at IV#2 (before the first SC infusion of IGSC 20%) and at SC Week#25	Specialty
Serum pregnancy test a	Qualitative serum $\beta$ -HCG for females of child-bearing potential will be performed at Screening and Final Visit	Central

**Table 3-2 Name, Description, and Location of Laboratory Tests and Procedures**

Test Panel	Description	Location
Urine pregnancy test	Qualitative urine pregnancy test for females of child-bearing potential will be performed at IV #1 Baseline	Local
Viral nucleic acid amplification technology (NAT) testing a, b	SC Week#1 prior to IGSC 20% infusion: Collect retain samples for hepatitis A virus (HAV) RNA, HBV DNA, HCV RNA, HIV RNA, and parvovirus B19 (B19V) DNA testing	Central
Viral serology testing a, b	SC Week#1 prior to IGSC 20% infusion: Collect retain samples for hepatitis A antibody differential (IgM/IgG), hepatitis B core antibody differential (IgM/IgG), hepatitis C antibody, HIV-1/-2 + Group O antibody, and B19V antibody differential (IgM/IgG) testing	Central
Urinalysis a	Microscopic evaluation is done only with cause. pH, protein, glucose, ketones, bilirubin, nitrites, urobilinogen, blood, leukocyte esterase (with microscopic examination of the urine if abnormal)	Central

a Samples collected for laboratory analyses that are non-analyzable due to any factor (ie, lost, quantity not sufficient, laboratory error) need to be recollected by contacting the subject and arranging for re-sampling.

b See [Section 3.6.3.2](#) for details.

### 3.6.3.1 Assessment and Recording of Infections

The site is to record non-serious infections (by category), which include infections of any kind including for example acute sinusitis, exacerbation of chronic sinusitis, acute otitis media, pneumonia, acute bronchitis, infectious diarrhea, etc., which will be recorded as an AE with the Investigator answering the following question affirmatively in the eCRF: “Is this an infection?” (verbatim term delineating nature of infection). Also record validated infections documented by positive radiograph, fever (>38°C oral or >39°C rectal), culture, or diagnostic testing for microorganisms eg, bacterial, viral, fungal, or protozoal pathogens (for instance, rapid streptococcal antigen test). The specific evaluations performed to validate infections must be recorded in the eCRF.

### 3.6.3.2 Virus Safety Testing

Virus safety (viral NAT and viral serology) retain samples collected at SC Week#1 prior to IGSC 20% infusion will be tested only if the subject exhibits clinical signs and symptoms consistent with HAV, HBV, HCV, HIV, or B19V infection while participating in the study. Virus safety samples will be retained until all analyses in support of the study are complete. Additional blood samples for viral NAT and viral serology testing may be collected and tested during the study only if the subject exhibits clinical signs and symptoms consistent with HAV, HBV, HCV, HIV, or B19V infection while participating in the study. Note: For pediatric subjects, at the discretion of the Investigator, virus safety retain samples may be drawn 1 or 2 days prior to SC Week#1 instead of combining with other blood draws on a single day.

### 3.6.3.3 D-dimer and Wells Score

The Wells Score for DVT and PE with associated citations is described in [Appendix 4](#) which provides full details for assigning point score for each of these individual conditions. At Screening and prior to administering IGSC 20% for the first time at the SC Week #1 Clinic Visit, Wells Score and blood draw for D-dimer will be performed to establish a pretreatment benchmark (prior to receiving IGIV-C 10% and prior to beginning IGSC 20%, respectively). At subsequent visits during the SC Phase, the Wells Score and blood draw for D-dimer will be performed only if the abbreviated physical exam and Specific Signs/Symptoms Check (defined in [Section 3.6.2.4](#)) raises any clinical/medical concerns regarding possible presence of DVT or PE.

As delineated in [Appendix 4](#), any subject with a total Wells prediction score >1 for the DVT assessment or >4 for the PE assessment should have further diagnostic testing per study site standard of care if medically indicated - unless the D-dimer is negative since this test has a high negative predictive value. If the D-dimer is positive at any time after the Screening time point (ie, above Screening value, exceeding cutoff range of the reporting laboratory), redraw a blood sample for repeat D-dimer testing at the central laboratory within one week to confirm. In all situations, the Investigator should use best medical judgment to evaluate the subject as medically indicated.

## 3.7 Removal of Subjects

Subjects will withdraw or be withdrawn from the study for the following reasons:

- At their own request or at the request of their legally acceptable representative
- If, in the Investigator's opinion, continuation in the study would be detrimental to the subject's well-being
- At the specific request of the Sponsor

Also, subjects will be withdrawn from IP/study drug or the study for the following reasons:

- Subjects with an occurrence of a concomitant disease, or any medical condition which, either because of its severity or duration or necessary change in treatment, contravenes the condition of the study or puts the subject at unnecessary risk or harm
- Subjects with an occurrence of an AE which in the opinion of the Investigator and/or subject requires termination of treatment
- Subjects who develop an SBI prior to the first dose of IGSC 20%
- Subjects who are noncompliant with the protocol per the Investigator's discretion
- Pregnancy

In all cases, the reason for withdrawal must be recorded in the eCRF and in the subject's source documentation.

If a subject discontinues study after receiving IGIV-C 10% but prior to receiving the first dose of IGSC 20%, an additional subject may be recruited into the study to assure that 30 adults and 12 children complete IGSC 20% treatment.

### **3.8 Follow-up of Subjects Withdrawn from Study**

Subjects who receive any amount of IP/study drug and discontinue early from the study will be requested to return clinic to have all assessments completed for the Early Termination Visit (see [Section 3.6.2.6](#) and [Appendix 1](#)) as close as practical to 1 week after their last administration of the IP/study drug.

### **3.9 Premature Termination of Study/Closure of Center**

The Sponsor, IRB/EC, and/or regulatory authorities have the right to close this study or a study center, and the Investigator/Sponsor has the right to close a center, at any time, although this should occur only after consultation among involved parties. The IRB/EC must be informed. Should the study/center be closed prematurely, all study materials (except documentation that has to remain stored at site) must be returned to the Sponsor. The Investigator will retain all other documents until notification given by the Sponsor for destruction.

A study center can be closed for the following reasons:

- Lack of enrollment
- Non-compliance with the requirements of the study protocol
- Non-compliance with International Conference on Harmonization Good Clinical Practice (ICH GCP)

#### **STOPPING RULES FOR THE STUDY AS A WHOLE:**

As a conservative measure, if 5 subjects on IGSC 20% develop an SAE of exactly the same type (ie, the same MedDRA [Medical Dictionary for Regulatory Activities] preferred term) which is not an infection or manifestation of an underlying disorder documented in medical history, then this would constitute an unanticipated clustering which could signal a potential safety concern. If this situation were to arise, the Sponsor will constitute a Safety Review Committee (SRC) whose members (from Grifols) will be impartial and independent of the clinical trial team. In cases where there is a clear medical plausibility supporting an uncommon clustering of SAEs of the same type (not including infections), and these sentinel SAEs are designated as ‘definitely related’, ‘probably related’, or ‘possibly related’ by both the Investigator and the SRC, consideration would be given to possibly discontinuing the study.

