10. The subject has a history of or current diagnosis of deep venous thrombosis or thromboembolism (eg, deep vein thrombosis, myocardial infarction, cerebrovascular accident or transient ischemic attack); history refers to an incident in the year prior to Screening or 2 episodes over lifetime.
11. The subject is currently receiving anti-coagulation therapy which would make SC administration inadvisable (vitamin K antagonists, nonvitamin K antagonist oral anticoagulants [eg, dabigatran etexilate targeting Factor IIa, rivaroxaban, edoxaban, and apixaban targeting Factor Xa], parenteral anticoagulants [eg, fondaparinux]).
12. The subject currently has a known hyperviscosity syndrome.
13. The subject has an acquired medical condition that is known to cause secondary immune deficiency, such as chronic lymphocytic leukemia, lymphoma, multiple myeloma, chronic or recurrent neutropenia (absolute neutrophil count less than  $1000/\mu\text{L}$  [ $1.0 \times 10^9/\text{L}$ ]), or human immunodeficiency virus (HIV) infection/acquired immune deficiency syndrome (AIDS).
14. The subject has a known previous infection with or clinical signs and symptoms consistent with current hepatitis B virus (HBV) or hepatitis C virus (HCV) infection.
15. The subject (if  $<18$  years of age) has non-controlled arterial hypertension at a level of greater than or equal to the 90th percentile blood pressure (either systolic or diastolic) for their age and height (See [Appendix 3](#)) or the adult subject has non-controlled arterial hypertension (systolic blood pressure  $>160$  mmHg and/or diastolic blood pressure  $>100$  mmHg)
16. The subject is receiving any of the following medications: (a) immunosuppressants including chemotherapeutic agents; (b) immunomodulators; (c) long-term systemic corticosteroids defined as daily dose  $>1$  mg of prednisone equivalent/kg/day for  $>30$  days.

Note: Intermittent courses of corticosteroids of not more than 10 days would not exclude

- a subject. Inhaled or topical corticosteroids are allowed.
17. The subject has known substance or prescription drug abuse
  18. The subject has participated in another clinical trial within 30 days prior to Screening (observational studies without investigative treatments [non-interventional] are permitted) or has received any investigational blood product with the exception of other IgG products within the previous 3 months

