#### **SC WEEKS #2, #3 CLINIC VISITS**

The objective of these 2 visits is for safety monitoring, for the subject/caregiver to self-administer SC infusions at the clinic, and for additional self-SC administration training and support by the clinical site staff to assure capability for full independent home administration.

- Abbreviated physical exam defined as targeted to symptoms and to include examination of heart, lungs, ears/nose/throat, and with inspection of previous injection sites, and Specific Signs/Symptoms Check for DVT or pulmonary embolus (PE).  
If the following specific signs/symptoms are present, perform Wells Score and blood draw for D-dimer testing ([Appendix 4](#); see also [Section 3.6.3.3](#)):
  - a. Clinical suspicion of possible DVT with unilateral symptomatic leg swelling, accompanied by any of the following pain, warmth, and/or redness
  - b. Medical suspicion of possible PE in a subject presenting with new or worsening dyspnea, tachypnea, chest pain, syncope, and cough in the appropriate clinical setting (cough should not be due to infection, lung disease [eg, asthma, emphysema], or angiotensin-converting enzyme inhibitors)
  - c. Any single alarm symptom such as hemoptysis or cyanosis ([36,37,38](#))
- Vital signs (pre-infusion: SBP, DBP, HR, T, RR)

- Predose Special tests (DAT, serum free hemoglobin, haptoglobin) will be performed at both SC Week #2 and SC Week #3 visits. (These visits represent a 7-day time point after the prior IGSC 20% infusion). Note that additional special tests (DAT, serum free hemoglobin, haptoglobin) will be performed 2-4 days *post SC #2 only* (also noted below as a separate Blood Sampling Visit).
- Observe subject/caregiver self-administration of SC infusion of IGSC 20% in the clinic  
Note: Site personnel will observe (and re-train if needed) subjects/caregivers on administration IGSC 20% using the infusion SC pump
- Concomitant medications
- Adverse events including SBIs  
Note: Record any SBIs (defined in [Appendix 2](#)), hospitalizations due to infections, and non-serious infections (by category) as detailed in [Section 3.6.3.1](#).
- Record days lost from work/school/daily activities due to infections and treatment
- Review SC infusion diary and infusion details with subjects/caregivers

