#### 4.3.7 Adverse Event and Pregnancy Documentation

All AEs and SAEs occurring after the subject has signed the ICF through the Final Visit (ie, end of study) must be fully recorded in the subject's eCRF or SAE form and medical record. If no AE has occurred during the study period, this should also be indicated in the eCRF.

It is the responsibility of the Investigator to ensure that AEs are appropriately recorded.

At each visit, AEs will be elicited by asking the individual a non-leading question such as "Do you feel different in any way since the last visit?" Moreover, AEs will also be collected through directly observed events or spontaneously volunteered by the subject. Clearly related signs, symptoms and abnormal diagnostic procedures should preferably be grouped together and recorded as a single diagnosis or syndrome wherever possible.

The following variables must be recorded in the AE eCRF:

1. the verbatim term (a diagnosis is preferred)
2. date/time of onset
3. date/time of resolution
4. severity (mild, moderate, severe)
5. causality (unrelated, doubtful/unlikely, possible, probable, definite)\*
6. seriousness (yes, no)
7. action taken (with regard to IP/study drug)
8. other action (to treat the event)
9. outcome and sequel (follow-up on AE)

\*Causality assessment will be made only when the AE occurs after the subject has initiated at least one infusion of the IP/study drug. An AE occurring before subject's exposure to IP/study drug will be always labeled as "unrelated".

For AEs that occur during infusions, the infusion rate in effect at the time of onset of the AE, the time of onset of the AE and the time of AE change materially in intensity and/or resolve will be captured in the eCRF.

In addition to the Investigator's own description of the AEs, each AE will be encoded according to the Medical Dictionary for Regulatory Activities (MedDRA).

For example, a laboratory test abnormality considered clinically relevant, eg, causing the subject to withdraw from the study, requiring treatment or causing apparent clinical

manifestations, or judged relevant by the Investigator, should be reported as an AE. Each event must be described in detail along with start and stop dates, severity, relationship to IP/study drug, action taken, and outcome. Each event must be adequately supported by documentation as it appears in the subject's medical or case file.

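### The safety-review trigger counts SAEs by identical preferred term, so DVT and PE, which the SC-Phase check watches for together, are tallied apart; a low-weight, cheaply mended weakness

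*Protocol*

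**What the plan says.** The rule stands in Protocol Section 3.9, under the stopping rules for the study as a whole. It is offered as a conservative safeguard and takes effect when 5 IGSC 20% recipients each "develop an SAE of exactly the same type (ie, the same MedDRA [Medical Dictionary for Regulatory Activities] preferred term) which is not an infection"; type is thus defined by the MedDRA preferred term. Infections and manifestations of a disorder already in the medical history are left out of the count. When the count is reached, the sponsor forms an SRC from its own staff outside the trial team; the SRC does not exist before then. If the cluster is medically plausible, and the investigator and the SRC both judge the events at least possibly related, "consideration would be given to possibly discontinuing the study".

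The SC-Phase visits in Section 3.6.2.4 include a "Specific Signs/Symptoms Check for DVT or pulmonary embolus (PE"). Section 3.6.3.3 asks for a Wells Score and a D-dimer draw when that check "raises any clinical/medical concerns regarding possible presence of DVT or PE". The same section and Appendix 4 score DVT and PE separately, with different cut-offs (>1 and >4).

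No section of the protocol pools related terms for the trigger or sets a separate thromboembolic trigger.

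**The concern.** This is the only numeric study-wide safety trigger in the protocol, and Section 3.9 presents it as conservative. DVT and PE are the pair for which the protocol sets up one shared check and one shared blood test during SC treatment. A cluster of DVT in some subjects and PE in others is therefore something the protocol looks for, but the trigger splits it into two smaller counts.

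At stake is the guarantee of a review outside the trial team once a cluster reaches 5 subjects. For a mixed DVT/PE cluster, that guarantee can be delayed until as many as 9 subjects are affected.

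**Working it through.** **Inputs.** Trigger: 5 subjects under one preferred term (Section 3.9). Planned enrolment: 50 (Section 5.2). Assumptions: DVT and PE code to exactly two preferred terms, and all events are eligible to count. The threshold of 5 has no stated derivation or error rate, so there is no figure of the plan to reproduce.

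**Largest cluster without a trigger.** Let a subjects have DVT only, b PE only and c both. The written rule stays silent while a + c ≤ 4 and b + c ≤ 4. The total a + b + c is largest at a = 4, b = 4, c = 0, which gives 8 subjects; 8/50 = 16%. Pooled, the rule stays silent up to 4 subjects; 4/50 = 8%. At 9 subjects one of the two terms must have at least 5, so both rules fire.

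**Chance that the written rule fires, given k affected subjects.** This needs no assumed event risk. With one event per subject and DVT share w,

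P(fires) = 1 − Σ C(k,i) wⁱ (1−w)ᵏ⁻ⁱ, summed over i with i ≤ 4 and k − i ≤ 4.

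For k = 5 this reduces to w⁵ + (1−w)⁵:
- w = 0.5: 0.03125 + 0.03125 = 0.0625
- w = 0.75: 0.2373 + 0.0010 = 0.2383
- w = 0.8: 0.3277 + 0.0003 = 0.3280

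The splits are assumptions.

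| Affected subjects | 50:50 | 75:25 | 80:20 | Pooled |
|---|---|---|---|---|
| 5 | 0.06 | 0.24 | 0.33 | 1 |
| 6 | 0.22 | 0.54 | 0.66 | 1 |
| 7 | 0.45 | 0.77 | 0.86 | 1 |
| 8 | 0.73 | 0.91 | 0.95 | 1 |
| 9 or more | 1 | 1 | 1 | 1 |

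Overlap narrows the gap. If 30% of affected subjects have both events and the rest divide evenly, each term has probability 0.65 per subject. With 5 affected subjects, P(fires) = 2 × 0.65⁵ − 0.3⁵ = 0.23; with 6 it is 0.60.

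**Chance of firing at an assumed overall risk p of a DVT/PE SAE, N = 50.** The protocol gives no event rate, so the values of p are illustrative. Pooled: 1 − Binomial CDF(4; 50, p). Written: 1 − P(DVT ≤ 4 and PE ≤ 4) under a multinomial with probabilities pw, p(1−w) and 1−p.

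| p | Pooled | Written, 50:50 | Written, 80:20 |
|---|---|---|---|
| 2% | 0.0032 | 0.0003 | 0.0012 |
| 3% | 0.0168 | 0.0018 | 0.0069 |
| 5% | 0.1036 | 0.0162 | 0.0491 |
| 10% | 0.5688 | 0.1986 | 0.3733 |

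At 2% to 3% neither rule is likely to fire, because the threshold of 5 dominates. The counting unit matters only if risk is well above that, which is the clustering the rule is meant to catch.

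**The case against.** The strongest reply is that the protocol states a clear, reproducible unit and applies it consistently. Checking for two conditions at one visit does not oblige anyone to count them as one SAE type, and separate Wells tables point the other way. Any rule based on preferred terms splits related events, and the protocol's own examples of "thromboembolism (eg, deep vein thrombosis, myocardial infarction, cerebrovascular accident or transient ischemic attack") reach beyond this pair. That stands as far as it goes: there is no contradiction, and the point is confined to DVT and PE because these are the two events the SC-Phase check names.

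A second reply is that Section 4.3.7 already handles grouping, since related findings "should preferably be grouped together and recorded as a single diagnosis or syndrome wherever possible". That concerns signs and symptoms within one subject's record. It does not join DVT in one subject to PE in another.

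A third reply is that little is lost when the trigger is missed. This largely stands. A reader might infer that 8 thromboembolic SAEs could pass unnoticed, or that the written rule prevents a timely stop. The documents do not support either reading. Every SAE goes to the sponsor within 24 hours (Section 4.4.1). The sponsor, IRB/EC or authorities may close the study at any time, and nothing in Section 3.9 forbids an earlier review. The trigger itself only convenes a committee. What is lost is the automatic step.

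**Conclusion.** The point holds as a low-weight design improvement. For a mixed DVT/PE cluster, automatic SRC review can be missed with up to 8 affected subjects, against 4 if pooled. At 5 affected subjects the written rule fires with probability 0.06 to 0.33 under the assumed splits and one event per subject.

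The figure of 8 should not be read as unconditional. It rests on exactly two preferred terms and no subject with both events. It would be higher with further venous-thrombosis terms, or if some events were set aside as manifestations of a documented disorder, and lower with overlap. The 16% uses planned enrolment. The trigger counts subjects on IGSC 20%, and that number is not fixed: Section 3.7 says that if a subject leaves "prior to receiving the first dose of IGSC 20%, an additional subject may be recruited into the study". Percentages of completers would use a group that the trigger does not refer to.

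The two rules differ only for clusters of 5 to 8 subjects, and at assumed risks of 2% to 3% the change makes almost no practical difference.

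**What to change.** Add one sentence to Section 3.9: for this rule, subjects on IGSC 20% with any SAE in a pre-listed grouping of DVT and PE preferred terms count as having the same type of SAE, each subject once. Leave the threshold of 5, the SRC action and preferred-term counting for all other SAEs as they are.

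The data are already collected, so the cost is the sentence and the term list. The downside is a slightly higher chance of convening the SRC for a chance cluster: at an assumed background risk of 2% and N = 50, 0.003 pooled against 0.0003 to 0.001 as written.
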